**B. 'Hypos' when you are asleep**

Never      Less than one a      About once or twice a      About once a week      About twice a      Most days

	Never	Less than one a month	About once or twice a month	About once a week	About twice a week	Most days
15. In the past 6 months , how often have you had a hypo during your sleep ?						
16. In the past 6 months , how often have you had a hypo during your sleep ...	Never	Less than one a month	About once or twice a month	About once a week	About twice a week	Most days
a) ... and were unable to treat yourself when you woke up?						
b) ... and someone else gave you sugar by mouth (e.g. a drink, carbohydrate, glucose gel)?						
c) ... and someone else gave you a glucagon injection?						
d) ... which led to a major problem (e.g. a fit, tongue biting, fall, collapse, incontinence)?						
e) ... where you stayed asleep and only later realised that you had been hypo?						
During my sleep...	Never	Rarely	Sometimes	Often	Always	Not Applicable
17. ... I have symptoms which wake me when my blood glucose is low						
18. ... other people recognise that I am hypo before I do						
19. ... my insulin pump / monitoring device wakes me when my blood glucose is low						
20. Is there anything else you would like to mention about your hypos or your awareness of hypos when you are asleep ? If so, please write it in this box.						

**Thank you. Please check that you have answered all the questions.**

**Appendix 4 - Hypoglycemia symptom questionnaires****Hypoglycemic symptoms during the hypoglycemic clamp**

Please rank your experience of the following SYMPTOMS on a scale from 1 to 7 where “1” means that you do not experience the symptom at all, while “7” means that you experience the symptom a great deal. Please place an “X” in ONLY ONE of the 7 boxes for each symptom.

SYMPTOM INTENSITY	Not at all	→	→	Moderate	→	→	A great deal
Inability to Concentrate	1	2	3	4	5	6	7
Blurry Vision	1	2	3	4	5	6	7
Anxiety	1	2	3	4	5	6	7
Confusion	1	2	3	4	5	6	7
Difficulty Speaking	1	2	3	4	5	6	7
Double Vision	1	2	3	4	5	6	7
Drowsiness	1	2	3	4	5	6	7
Tiredness	1	2	3	4	5	6	7
Hunger	1	2	3	4	5	6	7
Weakness	1	2	3	4	5	6	7
Sweating	1	2	3	4	5	6	7
Trembling	1	2	3	4	5	6	7
Warmness	1	2	3	4	5	6	7
Heart Racing	1	2	3	4	5	6	7

**Appendix 5 - Hypoglycemia questionnaires**

**The Gold Score**

1. Do you know when your hypos are commencing? Please circle a number:

	Always aware					Never aware	
Awareness	1	2	3	4	5	6	7

**Edinburgh Hypoglycaemia Survey**

2. Please score the extent to which you experience the following symptoms during a typical daytime hypoglycaemic episode (circle a number for each symptom)

	Not present					Present a great deal	
Confusion	1	2	3	4	5	6	7
Sweating	1	2	3	4	5	6	7
Drowsiness	1	2	3	4	5	6	7
Weakness	1	2	3	4	5	6	7
Dizziness	1	2	3	4	5	6	7
Warmth	1	2	3	4	5	6	7
Difficulty Speaking	1	2	3	4	5	6	7
Pounding heart	1	2	3	4	5	6	7
Inability to concentrate	1	2	3	4	5	6	7
Blurred vision	1	2	3	4	5	6	7
Hunger	1	2	3	4	5	6	7
Nausea	1	2	3	4	5	6	7
Anxiety	1	2	3	4	5	6	7
Tiredness	1	2	3	4	5	6	7
Tingling lips	1	2	3	4	5	6	7
Trembling	1	2	3	4	5	6	7
Headache	1	2	3	4	5	6	7

Comments:

## Guy's and St Thomas' Minimally Modified Clarke Hypoglycaemia Survey

2. Tick the category that best describes you (tick one only):
- I always have symptoms when my blood sugar is low
- I sometimes have symptoms when my blood sugar is low
- I no longer have symptoms when my blood sugar is low
2. Have you lost some of the symptoms that used to occur when your blood sugar was low?
- Yes  No
9. In the past 6 months, how often have you had hypoglycaemic episodes, where you might feel confused, disorientated, or lethargic and were unable to treat yourself?
- Never  Once or twice  Every other month
- Once a month  More than once a month
10. In the past year, how often have you had hypoglycaemic episodes, where you were unconscious or had a seizure and needed glucagon or intravenous glucose?
- Never  5 times  10 times
- 1 time  6 times  11 times
- 2 times  7 times  12 or more times
- 3 times  8 times
- 4 times  9 times
11. How often in the last month have you had readings <3.5mmol/l with symptoms?
- Never  1-3 times  1 time/week
- 2-3 times/week  4-5 times/week  Almost daily
12. How often in the last month have you had readings <3.5mmol/l without any symptoms?
- Never  1-3 times  1 time/week
- 2-3 times/week  4-5 times/week  Almost daily
13. How low does your blood sugar need to go before you feel symptoms?
- 3.4-3.9mmol/l  2.8-3.3mmol/l  2.2-2.7mmol/l  <2.2 mmol/l
14. To what extent can you tell by your symptoms that your blood sugar is low?
- Never  Rarely  Sometimes  Often  Always

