Auto Mode: The MiniMed 670G Insulin Pump is capable of continuous insulin delivery, at set and variable rates, for the management of diabetes mellitus in persons requiring insulin. When used with the CGM components (Guardian 3 sensor and transmitter), the pump system is capable of continuous or periodic monitoring of glucose levels in the interstitial fluid under the skin and detection of possible low or high blood glucose episodes. The pump also displays continuous glucose values, storing this data so that it can be retrospectively analyzed to track patterns and improve diabetes management. These features are similar to the commercially available Medtronic sensor-enabled system. The MiniMed 670G Insulin Pump also includes the closed loop algorithm and SmartGuard feature that may be enabled by the user. The SmartGuard feature enables insulin to suspend before a sensor glucose threshold is reached. The closed loop and SmartGuard feature will not be active at the same time. When closed loop is enabled on the MiniMed 670G insulin pump, the sensor glucose values received from the transmitter by the insulin pump will be used to automatically calculate the insulin dose. It will then deliver insulin to the patient, at five minute intervals, to achieve glycemic control. This is in addition to user-defined insulin boluses that patients will continue to require for meals. When Closed Loop is not enabled, the user may have the SmartGuard feature enabled. Here it will suspend basal rate delivery before the sensor glucose value has reached the programmed low threshold.

Manual Mode: If neither the Closed-Loop nor the SmartGuard features are enabled, the pump will deliver pre-programmed basal rates without modulation by the sensor. In this way, manual mode functions like any other insulin pump system. That is, there is no change in the level of technology when compared to the subject's existing insulin pump. The only exception to this is if the SmartGuard feature is enabled, which will be determined by experienced study clinicians.

Basal-IQ: The Basal-IQ feature helps reduce the frequency and duration of low-glucose events by predicting glucose levels 30 minutes ahead and suspending insulin if the patient is expected to drop below 80 mg/dL or if glucose is currently below 70 mg/dl and falling. The system resumes basal insulin delivery once glucose values start to rise.

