**b) MRS studies and hyperinsulinemic hypoglycemic clamps (Magnetic Resonance Research Center)**

Subjects will be asked to remain fasting from midnight prior to the study and to check their blood glucose at home before bed and on awakening to ensure that the glucose level is above 70mg/dl and below 200mg/dl. They will be

**Figure 5: Overall Study Design.** A) Following a 1 week of CGM screening for hypoglycemia, eligible T1DM patients will undergo 4 weeks of CGM for run-in and then will be randomized to 8-10-week therapy with PLGS insulin pump in either auto or manual mode. B) MRS study with timeline for hyperinsulinemic-hypoglycemic clamp and carbon-13 tracer infusion.

instructed to call [name] with any readings outside of this range. Upon arrival to the MRRC (7:30AM), their blood glucose will be checked as a safeguard, and insulin received via the insulin pump will be held. An IV catheter will be inserted for infusion of insulin and glucose to maintain normal glucose levels. A urine pregnancy test will be completed on all female subjects of child bearing potential. Any female testing positive will be excluded from the study. A second IV catheter will be inserted for arterialized venous blood sampling and then patients will be placed in the scanner for MRS. MRS measurement will be performed under clamped insulin-induced hypoglycemia as described below. At the end of the clamp procedure, a symptom questionnaire will be administered, asking the subjects to rate the intensity of their symptoms on a scale from 0 to 7 (none to severe) [13] (Appendix 4). Neuroglycopenic (dizziness, tingling, blurred vision, difficulty in thinking, faintness) and autonomic symptoms (anxiety, palpitations, hunger, sweating, irritability, or tremor) are included in this assessment, which has been well validated over time. The visit will last no longer than 4 hours, including ~130 minutes of hypoglycemic clamp and MR spectroscopy.

After 8 weeks, both groups will undergo repeat MRS assessment of brain metabolism study according to the same procedures. They will then resume their previous out-patient care via insulin pump.

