Inclusion criteria:

- Provide signed and dated informed consent form
- Male or female
- Age 50-80 years (at least 50% over the age of 65)
- T1DM (>10 years duration)
- C-peptide undetectable
- HbA1c of < 8%
- History of frequent hypoglycemia with unawareness (defined as 2 or more episodes of severe hypoglycemia within one year requiring assistance) and 2 or more glucose values < 54 mg/dL during the week of Continuous Glucose Monitoring (CGM) (iPRO monitor, Medtronic) prior to enrollment
- BMI <35 kg/m^2
- Good general health as evidenced by medical history and blood screening
- Willing to comply with all study procedures and be available for the duration of the study
- Willing to fast for a limited time period on the morning of a clamp study

Exclusion Criteria

- Significant diabetic complications (untreated proliferative retinopathy, creatinine  $\geq 1.5$  mg/dl, urinary albumin levels 300 mg/day, autonomic neuropathy, painful peripheral neuropathy)
- Significant alcohol intake and vegetarian diet since both are known to have an impact on counterregulation and brain metabolism
- Any contraindications for MRI scanning, including presence of metallic implants or claustrophobia.
- Heavy exercise on a regular basis (i.e. marathon runners)

- Known allergic reactions to components of the study product(s)
- Treatment with another investigational drug or other intervention
- Active infection including hepatitis C, hepatitis B, HIV
- Any past or current history of alcohol or substance abuse
- Psychiatric or neurological disorders under active treatment
- Weighing less than 110 lbs
- Baseline hemoglobin < 10.5 g/dL in females, or < 12.5 g/dL in males.
- Blood donation within 30 days of the study
- History of coagulopathy or medical condition requiring long-term anticoagulant therapy (low-dose aspirin treatment is allowed)
- Co-existing cardiac, liver, and kidney disease
- Abnormal liver function tests
- Women who are pregnant (as assessed by pregnancy test that will be performed on female participants at reproductive age), planning to become pregnant, or lactating.
- Any medical condition or medication that, in the opinion of the investigators, will interfere with the safe completion of the study or study outcomes

8. How will **eligibility** be determined, and by whom?

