5. In the past month , have you had blood glucose readings (in mmol/l) ...	If yes , how often did you have hypo symptoms?					
	Never	Rarely	Sometimes	Often	Always	
a) ... 3.5 to 3.9?    Yes  No  Don't know 						
b) ... 3.0 to 3.4?    Yes  No  Don't know 						
c) ... 2.5 to 2.9?    Yes  No  Don't know 						
d) ... less than 2.5?    Yes  No  Don't know 						

6. How low does your blood glucose usually need to be before you feel any of the following symptoms?	4.0mmol/l or above	3.5-3.9 mmol/l	3.0-3.4 mmol/l	2.5 -2.9 mmol/l	Below 2.5mmol/l	I do not have these symptoms
a) Trembling, shakiness, pounding heart, warmth, sweating, hunger						
b) Weakness, lack of coordination, confusion, dizziness, inability to concentrate, difficulty speaking, blurred vision, drowsiness, tiredness, irritability, odd behaviour						
c) Nausea, tingling, headache						

	Never	Rarely	Sometimes	Often	Always
7. I have symptoms when my blood glucose is low					

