**Adult Low Blood Sugar Survey (University of Virginia) / Fear of Hypoglycaemia Survey**

I. **Behaviour:** Below is a list of things people with diabetes sometimes do in order to avoid low blood sugar and its consequences. Tick the box that best describes what you have done during the last 6 months in your daily routine to AVOID low blood sugar and its consequences. **(Please do not skip any!).**

To avoid low blood sugar and how it affects me, I ...	Never	Rarely	Sometimes	Often	Almost always
1. ate large snacks					
2. tried to keep my blood sugar 4mmol/L or above					
3. reduced my insulin when my blood sugar was low					
4. measured my blood sugar six or more times a day					
5. made sure I had someone with me when I go out					
6. limited my out of town travel					
7. limited my driving (car, truck or bicycle)					
8. avoided visiting friends					
9. stayed home more than I liked					
10. limited my exercise / physical activity					
11. made sure there were other people around					
12. avoided sex					

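### The glucose-dependent items on three self-completed forms are printed only in mmol/L, while the protocol works only in mg/dL and gives no conversion

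*Combined protocol and SAP*

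**What the plan says.** **The forms.** Three self-completed instruments in the appendices name glucose values, always in mmol/L.

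- Guy's and St Thomas' Minimally Modified Clarke survey (Appendix 5). Items 11 and 12 use a cut-point of 3.5 mmol/l; item 12 reads "How often in the last month have you had readings <3.5mmol/l without any symptoms". Item 13, "How low does your blood sugar need to go before you feel symptoms", offers four bands: 3.4-3.9, 2.8-3.3, 2.2-2.7 and <2.2 mmol/l.
- Hypo Awareness Questionnaire (Appendix 3). Item 5 asks "have you had blood glucose readings (in mmol/l") in bands 3.5 to 3.9, 3.0 to 3.4, 2.5 to 2.9 and below 2.5. Item 6, "How low does your blood glucose usually need to be before you feel any of the following symptoms", uses the same bands plus 4.0 or above.
- Fear of Hypoglycaemia Survey (Appendix 5). Item 2 reads "tried to keep my blood sugar 4mmol/L or above".

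**The protocol body.** Glucose is in mg/dL throughout.

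- Home checks before the scan (Section I, 3.b): "to ensure that the glucose level is above 70mg/dl and below 200mg/dl".
- CGM entry criterion (Section I, inclusion criteria): "2 or more glucose values < 54 mg/dL during the week of Continuous Glucose Monitoring (CGM".
- Basal-IQ description (Section I, item 3): insulin is suspended if glucose is "expected to drop below 80 mg/dL or if glucose is currently below 70 mg/dl and falling".
- The clamp targets and the discharge level in Section I, 3.b are also in mg/dL.

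**Use of the forms.** Section I, 3.a sends the screening assessment of unawareness to Appendix 3. Section I, 3.c uses questionnaires around each MRS study to gauge the degree of unawareness. Section I, item 5 adds interviews and the Ryan, Gold and Clarke instruments, compared with episodes on blinded CGM. The Schedule of Events lists hypoglycemia questionnaires at all five visits, without saying which form is used when.

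**The concern.** The affected items are the ones that tie symptoms to a glucose level, which is the core of hypoglycemia awareness. Clarke 11 and 12, which ask how often low readings came with and without symptoms, are also the items closest to the CGM record they are to be compared with. That record is judged in mg/dL and the items are in mmol/L.

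The numbers differ by a factor of about 18, so a person used to mg/dL has to convert before placing a remembered reading in a printed band. The participants are 50 to 80 years old, at least half of them over 65, and no conversion aid is described. Clarke 11 to 13 offer no don't-know option, so a wrong answer leaves no trace on the form.

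Restoring awareness is named in the Statement of Purpose, and the trial plans only 15 participants per group. Avoidable error in this outcome is costly at that size.

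**Working it through.** The plan states no figure on this point, so there is nothing to reproduce. The check compares units, counts items and converts.

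**1. Units.** Every glucose value in the protocol body (home range, CGM criterion, pump thresholds, clamp, discharge) is in mg/dL. Every glucose value on the three forms is in mmol/L. I found no mg/dL equivalent, conversion table or staff instruction.

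**2. Count of affected items.**

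- Clarke: items 11, 12 and 13, so 3 of 8 printed items.
- Hypo Awareness Questionnaire: 5a-d and 6a-c, so 4 + 3 = 7 response rows.
- Fear survey: item 2, so 1 of 33. It asks how often a behaviour was used and does not ask for a reading.
- The Gold score, the Edinburgh survey and the clamp symptom scale name no glucose value.

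**3. Conversion.** mg/dL = mmol/L × 18.016. The factor is an outside constant, not in the documents.

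| mmol/L | 2.2 | 2.5 | 2.7 | 2.8 | 2.9 | 3.0 | 3.3 | 3.4 | 3.5 | 3.9 | 4.0 |
|---|---|---|---|---|---|---|---|---|---|---|---|
| mg/dL | 39.6 | 45.0 | 48.6 | 50.4 | 52.2 | 54.0 | 59.5 | 61.3 | 63.1 | 70.3 | 72.1 |

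Factors of 18.0 and 18.02 change these by no more than about 0.1 mg/dL. The trial's own entry threshold of 54 mg/dL is 3.0 mmol/L, a band edge on the Hypo Awareness Questionnaire.

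**4. Closing the bands.** Converting only the printed edges of the Hypo Awareness bands gives 63-70, 54-61 and 45-52, which leaves 71, 62 and 53 mg/dL in no band. To assign them, divide by 18 and round to the form's 0.1 mmol/L:

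- 71/18 = 3.94, so 3.9
- 62/18 = 3.44, so 3.4
- 53/18 = 2.94, so 2.9

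The bands are therefore 63-71, 54-62, 45-53 and <45, with 72 or above for item 6 (72/18 = 4.0). For Clarke 13, 61/18 = 3.39 (3.4), 60/18 = 3.33 (3.3), 50/18 = 2.78 (2.8), 49/18 = 2.72 (2.7) and 40/18 = 2.22 (2.2), which gives about 61-71, 50-60, 40-49 and <40. One value is ambiguous: 39 mg/dL lies below the converted cut-point of 39.6 but rounds to 2.2 (39/18 = 2.17). The choice hardly matters but should be fixed in print.

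**5. What depends on these items.** The inclusion criterion for hypoglycemia with unawareness rests on severe episodes and CGM values, not on a questionnaire score. The only test in the Statistical Considerations is on acetate utilization, and the sample size and alpha belong to that test. What remains exposed is awareness as an outcome and as a description of the sample.

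**The case against.** The strongest reply is that the items can be answered once someone divides by 18. The forms are tied to study visits, and awareness is also assessed by detailed interviews and compared with CGM, so the trial does not rely on unaided answers alone. Only some items are affected, and both arms complete the same forms.

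Much of this stands. It is why the point is about reliability and why it is limited to the items listed. It does not remove the problem: interviews and CGM supply no conversion on the form, and any help given by staff is unscripted.

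A reader might infer more than the documents support:

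- **That the items cannot be answered at all.** They can be, after conversion.
- **That participants will tick *Never*, or that staff will help at one visit and not another and so create false change.** The documents say nothing about either.
- **That the wrong people would be enrolled.** No questionnaire score is an entry criterion.
- **That the treatment comparison is biased.** Identical forms in both arms point to noise and misclassification, and nothing shows a difference by arm.

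**Conclusion.** The forms are in the wrong unit for this trial and should be corrected. The mismatch is certain from the text: 3 of 8 Clarke items, 7 response rows of the Hypo Awareness Questionnaire and 1 of 33 Fear items are in mmol/L, against a protocol entirely in mg/dL.

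The consequence is avoidable measurement error in hypoglycemia awareness, a stated aim, and in the questionnaire description of unawareness at screening. Its effect on a score cannot be sized, because the documents give no scoring rule for the Clarke survey or the Hypo Awareness Questionnaire.

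The conclusion rests on one inference: that participants read glucose in mg/dL. The documents do not state what their devices display, but the home-check range, the pump thresholds and the single US site all point that way.

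**What to change.** Print mg/dL equivalents on all three forms, and use the same version at screening and both assessments.

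- **Clarke 11 and 12:** <63 mg/dL.
- **Clarke 13:** about 61-71, 50-60, 40-49 and <40 mg/dL.
- **Hypo Awareness 5:** 63-71, 54-62, 45-53 and <45 mg/dL.
- **Hypo Awareness 6:** the same bands, plus 72 or above.
- **Fear item 2:** 72 mg/dL or above.

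If any forms have already been completed in mmol/L, flag these items and show as a sensitivity check whether the awareness results depend on them. State how the score is formed without them, since removing 3 of 8 Clarke items may not leave a comparable score.

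The cost is reprinting three forms and a minor IRB modification, with no added visit or assessment.

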## Diabetes Treatment Satisfaction Questionnaire: DTSQs

The following questions are concerned with the treatment for your diabetes (including insulin, tablets and/or diet) and your experience over the past few weeks. Please answer each question by circling a number on each of the scales.

1. How satisfied are you with your current treatment?

very satisfied                    6    5    4    3    2    1    0                    very dissatisfied

2. How often have you felt that your blood sugars have been unacceptably high recently?

most of the time                    6    5    4    3    2    1    0                    none of the time

3. How often have you felt that your blood sugars have been unacceptably low recently?

most of the time                    6    5    4    3    2    1    0                    none of the time

4. How convenient have you been finding your treatment to be recently?

very convenient                    6    5    4    3    2    1    0                    very inconvenient

5. How flexible have you been finding your treatment to be recently?

very flexible                    6    5    4    3    2    1    0                    very inflexible

6. How satisfied are you with your understanding of your diabetes?

very satisfied                    6    5    4    3    2    1    0                    very dissatisfied

7. Would you recommend this form of treatment to someone else with your kind of diabetes?

Yes, I would definitely                    6    5    4    3    2    1    0                    No, I would definitely  
recommend the                                                                                                                                                         not recommend the  
treatment                                                                                                                                                         treatment

8. How satisfied would you be to continue with your present form of treatment?

very satisfied                    6    5    4    3    2    1    0                    very dissatisfied

## Insulin Treatment Satisfaction Questionnaire (ITSQ) – abridged version

People who take insulin can have many different experiences with their treatment. Some people who take insulin may find it difficult and burdensome, while others feel that it is not much of a bother at all. The following questions are about your perceptions of your current insulin treatment and how it affects you in your daily life. When you think of your insulin treatment, please keep in mind the type of insulin you take, the dose or amount of insulin, your schedule for taking insulin, and the device or method you use to give yourself insulin.

Please think about your experiences during the **past 4 weeks** when you answer the questions.

Please answer each question by circling the number ① that best represents your answer. If you are unsure about how to answer a question, please give the best answer you can.

1. **How confident are you that you can avoid symptoms of low blood sugar (such as sweating, trembling, dizziness, blurred vision) with your current insulin treatment?**
- Extremely confident Not at all confident
- 1      2      3      4      5      6      7

2. **How confident are you that you can avoid severe episodes of low blood sugar that result in loss of consciousness (fainting or passing out) with the insulin you currently use?**
- Extremely confident Not at all confident
- 1      2      3      4      5      6      7

3. **In general, how bothered are you by symptoms of low blood sugar (such as sweating, trembling, dizziness, blurred vision) due to the insulin you currently use?**
- Not at all bothered Extremely bothered
- 1      2      3      4      5      6      7

4. **How much do you feel that the insulin you are currently using increases the chances that you will experience low blood sugar?**
- Not at all Extremely
- 1      2      3      4      5      6      7

5. **How worried are you about experiencing low blood sugars during the night with the insulin you currently use?**
- Not at all worried Extremely worried
- 1      2      3      4      5      6      7

The following questions are about your perceptions of your current method of taking insulin and how it affects you in your daily life. For these questions, you should only think about the device or method you use to give yourself insulin.

6. **How easy is it for you to take the correct amount of insulin each time with your current method of taking insulin?**  
Extremely easy Not at all easy  
1 2 3 4 5 6 7
7. **How convenient is your current method of taking insulin when you are away from home?**  
Extremely convenient Not at all convenient  
1 2 3 4 5 6 7
8. **How much pain or other physical discomfort do you experience with your current method of taking insulin?**  
No pain or discomfort A tremendous amount of pain or discomfort  
1 2 3 4 5 6 7
9. **How comfortable are you taking insulin in a public place (where people might see you with your current method of taking insulin)?**  
Extremely comfortable Not at all comfortable  
1 2 3 4 5 6 7
10. **How much emotional distress or anxiety do you experience related to your method of taking insulin?**  
No distress or anxiety A tremendous amount of distress or anxiety  
1 2 3 4 5 6 7
11. **Overall, how satisfied are you with your current method of taking insulin?**  
Extremely satisfied Not at all satisfied  
1 2 3 4 5 6 7

